## C. Study Design and Research Methods

Potentially eligible subjects will be screened during routine clinic visits or over the telephone. Potentially eligible and interested subjects will return for informed consent and a screening/baseline visit. No research procedures will occur prior to consent, including the MOCA.

After obtaining informed consent, participants will undergo a graded exercise test to screen for potential underlying cardiovascular disease. V02 peak will be measured at this time to develop the exercise prescription. All participants will begin with a low intensity lead-in for 1-2 weeks, then advance to a moderate intensity exercise during first 12 weeks. Randomization to continue on moderate versus advance to high intensity will occur at week 13.

**1. Consent & baseline visit.** After obtaining consent, the participant will be evaluated

-After obtaining consent, the participant will be evaluated by

- medical history, physical examination including vital signs
- Montreal Cognitive Assessment (MOCA)
- Resting BP, 12-lead resting ECG, and then a graded exercise test (GXT) administered by research personnel and a clinician experienced in exercise stress testing of older adults ([name]) to screen out volunteers with evidence of ischemic heart disease, serious arrhythmias, or abnormal HR/BP responses to exercise. Briefly, the test will begin at a comfortable walking speed and 0% elevation; speed will be maintained and the grade increased by 2% every 2 min, until the participant reaches 85% of age-predicted maximal heart rate or the test is otherwise terminated. The absolute and relative indicators for terminating an exercise test that are recommended by the American College of Sports Medicine (ACSM) will be employed.
- Baseline physical function assessments will be administered.

**2. Procedure visit #1 (within 14 days of visit #1).** All participants will arrive between 7:30-8am for:

- DXA scan
- Vital signs
- Anthropometrics (waist/hip circumference)
- Blood draw (fasting)
- 36 (up to 46, if needed to ensure 36 paired biopsy samples) volunteer participants (18 HIV+/18 HIV-) will have a muscle biopsy
  - If muscle biopsy at the end of the study cannot be done (patient refuses, change in medications, etc), then the number of biopsies will increase to a maximum of 46 in order to ensure each group has at least 18 paired (entry/completion) biopsy samples.
- Questionnaires

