**2. Exercise testing and training:** All exercise intervention components will include 3 to 4 weekly, supervised sessions of combined CEx + REx at the University of Colorado-Denver (UCD) Exercise Research Laboratory (ERL). All participants will begin with a 2-week supervised, low-intensity exercise acclimation with an experienced research assistant. The initial goal will be to walk on a treadmill for 20-30 continuous minutes at low-intensity (30-40% of maximal aerobic power [VO2max]) and complete 3 sets of 8 repetitions at low-intensity (40-50% of the one-repetition maximum; 1-RM) 3 or 4 days/week. This will facilitate comfort with study equipment and minimize injury.

At 2 weeks, all participants will complete an additional 10 weeks of moderate- intensity exercise, with a goal of 50 minutes of cardiovascular + 3 sets of 8 resistance exercises by the end of the 12 week initial intervention. This will ensure that every participant meets at least the DHHS-PA recommendations in a supervised setting. At week 13, participants will be randomized to continue moderate intensity exercise, or progress to a high-intensity intervention for an additional 12 weeks.

*Maximal aerobic power (VO2 max).* The measurement of VO2max (or peak) will be used to formulate the prescription for CEx at the screening visit. Increases in VO2max in response to exercise training will also verify that the exercise was of sufficient intensity to induce cardiorespiratory adaptations. During an initial 5-min warm-up, walking speed will be adjusted to elicit a HR that is ~70% of maximal HR (from the screening GXT). Speed will then be held constant and the grade of the treadmill will be increased by 2% every 2 minutes until volitional exhaustion or until the test is stopped (see section 4.1.2b). The O2 and CO2 content of expired air will be measured continuously by open circuit spirometry and averaged every 30 sec using an automated online system (TrueMax 2400; ParvoMedics, Sandy, UT). Objective evidence that VO2max has been attained will include at least 2 of the following: a plateau in VO2 despite an increased energy demand, a respiratory exchange ratio in excess of 1.10, and a maximal HR within 10 beats of the age-predicted value. In the absence of these benchmarks, the maximum measured VO2 will be deemed VO2 peak.

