Risks: The potential risks of exercise testing and training include development of ventricular arrhythmia, myocardial

infarction, cardiac arrest, and death, as well as the less serious problems of injury to tendons, ligaments, joints, and muscles.

Plans to minimize risk: The risks of exercise testing and training will be minimized by adhering to the following strategies:

**Endpoints for exercise tests:** In asymptomatic individuals who do not develop cardiovascular abnormalities, the endpoint for the maximal exercise tests will be achieving 85% of age-predicted maximal heart rate, fatigue that forces cessation of exercise, or increasingly unstable gait. The criteria that will be used to stop the exercise test before meeting the above criteria include the development of: (a) ST-segment depression of more than 0.2 mV that is either horizontal, downsloping, or slowly upsloping (less than 1 mV/sec) and lasts for 0.08 sec, or ST-segment elevation greater than 0.1 mV; (b) chest pain or discomfort; (c) serious arrhythmias, including multifocal PVCs, ventricular tachycardia, or sustained atrial tachyarrhythmias; (d) development of A-V block or other conduction defects; (e) a fall of systolic blood pressure of 10 mmHg or greater from the peak level with increasing exercise intensity; (f) diastolic blood pressure above 110 mmHg or systolic above 220 mmHg; (g) dizziness; (h) ataxic gait; and (i) pallor or cyanosis. If a subject is noted to have osteoporosis (T-score <-2.5, upon screening, he or she will be referred to their primary care physician to discuss the potential risks and benefits of exercise and the need for immediate or delayed treatment for osteoporosis prior to initiating the study. The risks associated with the muscular strength tests are musculoskeletal pain, fatigue, dizziness, and syncope. These risks will be minimized by providing one-on-one instruction in proper exercise technique on multiple days prior to testing. Workloads will be increased gradually to elicit moderate to maximal effort, and a brief rest period will follow each attempt. Appropriate warm-up and cool-down periods will be included in the strength test procedures. The potential for a serious adverse event to occur with resistance exercise testing is minimal in persons who have undergone prior medical screening. In 20,000 maximal dynamic strength tests in women and men aged 18 to 93 yr, no cardiovascular events were reported [140].

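### The 85% heart-rate stop is written for the maximal exercise tests with no exemption for the VO2 test, which the protocol elsewhere runs to exhaustion

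*Combined protocol and SAP*

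**What the plan says.** Three places in the protocol bear on when the VO2 test ends.

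- **Section IV.C, opening paragraphs and item 1 (consent and baseline visit).** After consent, participants have a graded exercise test (GXT) to screen for heart disease, and "V02 peak will be measured at this time to develop the exercise prescription". Item 1 ends the GXT at 85% of age-predicted maximal heart rate unless it is terminated for another reason.
- **Section IV.D.2, maximal aerobic power.** The treadmill grade rises "until volitional exhaustion or until the test is stopped (see section 4.1.2b"). A true maximum is accepted when two of three signs are present, one being "a maximal HR within 10 beats of the age-predicted value". Otherwise the highest value measured is called VO2 peak. The result "will be used to formulate the prescription for CEx at the screening visit", and increases in it "in response to exercise training will also verify that the exercise was of sufficient intensity to induce cardiorespiratory adaptations".
- **Section IV.D.2, endpoints for exercise tests.** For participants without symptoms or cardiovascular abnormalities, "the endpoint for the maximal exercise tests will be achieving 85% of age-predicted maximal heart rate", or fatigue, or unstable gait. A list of earlier safety stops follows.

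VO2 is measured again at week 13, to reset the prescription, and at week 23 (Section IV.C, items 6 and 7). The data analysis plan (Section F) lists VO2 peak as a secondary outcome. Section G uses it to check that a null chair-rise result is not a limit of that test's sensitivity.

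**The concern.** The VO2 procedure and the endpoint paragraph give different answers for a participant who reaches 85% of predicted heart rate and is not yet tired. Under the first, the test continues; under the second, it is over. The only treadmill test that the protocol describes as maximal is the VO2 test, so a plain reading of the endpoint paragraph covers it. The pointer that might settle the matter, section 4.1.2b, does not appear under that number in the text available.

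If the cap were applied, the VO2 recorded for such a participant would be below the true maximum. That value sets the cardiovascular dose at baseline and again at week 13, when intensity is randomised. It is also a secondary outcome and the stated evidence that training was hard enough. The fallback label VO2 peak would not distinguish a test ended by the heart-rate rule from one ended by fatigue.

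**Working it through.** **1. Can a test stopped at 85% meet the heart-rate sign?**

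Inputs: the 85% stop (endpoint paragraph), the 10-beat margin (maximal aerobic power paragraph) and ages 50 to 75 (Section IV.B). The documents name no prediction equation, so I assume 220 − age and repeat the check with 208 − 0.7 × age.

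Let M be the predicted maximum. The stop is 0.85M and the sign needs at least M − 10. The stop meets the sign only if 0.15M ≤ 10, that is M ≤ 10/0.15 = 66.7 bpm.

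| Equation | Age | M | 85% stop | Sign needs | Shortfall |
|---|---|---|---|---|---|
| 220 − age | 50 | 170 | 144.5 | 160 (94.1% of M) | 15.5 |
| 220 − age | 75 | 145 | 123.25 | 135 (93.1% of M) | 11.75 |
| 208 − 0.7 × age | 50 | 173 | 147.05 | 163 (94.2% of M) | 15.95 |
| 208 − 0.7 × age | 75 | 155.5 | 132.175 | 145.5 (93.6% of M) | 13.325 |

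No predicted maximum in this age range comes near 66.7 bpm. A test ended on reaching 85% therefore cannot show this sign under either equation. The protocol's own criterion presupposes an uncapped test.

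**2. Does any text limit the 85% stop to screening?**

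- The maximal aerobic power paragraph sets its warm-up from "maximal HR (from the screening GXT"). This treats the GXT as a separate, earlier test but says nothing about which stop applies to the VO2 test.
- The training-of-personnel paragraph distinguishes screening treadmill tests from later tests for supervision only.
- The endpoint paragraph speaks of maximal exercise tests in general.

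The separation of the two tests can be inferred. The limit on the stop is not written anywhere.

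**3. What would a capped VO2 do to the dose?**

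Let r be a capped participant's VO2 at the stop divided by the true maximum. The true intensity is then the labelled intensity × r. The value of r is not in the documents, so only break-even points follow from the protocol's bands: lead-in "at low-intensity (30-40% of maximal aerobic power"), moderate 40-50% and high 60-70%.

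- Bottom of the high band falls to the top of the moderate label: 60r ≤ 50, so r ≤ 0.833.
- Whole moderate band falls to the lead-in ceiling or below: 50r ≤ 40, so r ≤ 0.80.

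Over an assumed range of r from 0.75 to 0.90, the high band would be between 45-52.5% and 54-63% of true maximum, and the moderate band between 30-37.5% and 36-45%. These figures show sensitivity to r and are not estimates. The share of participants who would be capped is also unknown.

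**The case against.** The strongest reply is that the protocol already specifies an uncapped VO2 test. Only the maximal aerobic power paragraph gives the VO2 procedure, and it runs to exhaustion. Its warm-up speed comes from the GXT, and a test cannot take its warm-up from itself. The statement in Section IV.C that VO2 peak is measured at this time may mean at that visit and not during the GXT. The endpoint paragraph may be one list serving two tests, with 85% meant for the GXT and fatigue for the VO2 test. The absence of a second baseline treadmill test from the visit lists proves little, because the itemised baseline list omits VO2 altogether. I accept this as the likely intention. It does not remove the conflict, because the endpoint paragraph offers 85% as a terminal endpoint for maximal tests without saying which one.

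A reader might infer three stronger points that the documents do not support.

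- **That the VO2 tests will be capped.** The text permits this reading but does not establish it. Participants who tire or become unsteady before 85% are unaffected either way.
- **That the VO2 gain will be inflated.** A capped baseline followed by uncapped later tests would show a false gain of 1/r − 1, which is 11% at r = 0.90 and 25% at r = 0.80. This needs the GXT stop to govern at baseline and the endpoint paragraph to be ignored later. If the endpoint paragraph governs, all three tests are capped; if the VO2 procedure governs, none is.
- **That the randomised comparison collapses.** For a given r the ratio of the bands is unchanged: 60r/40r = 1.5. The absolute gap shrinks from 20 to 20r percentage points, but the ordering holds. Resistance dosing uses 1-RM, and chair-rise measurement does not depend on VO2. Bias between arms or HIV groups would require the capped share to differ, and nothing in the documents indicates that it does.

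**Conclusion.** The concern holds as a conflict between stated rules. An 85% stop, applied as the endpoint paragraph is worded, is incompatible with the VO2 procedure and makes one of its three signs of a maximum unattainable at ages 50 to 75. The shortfall is 11.75 to 15.5 beats under 220 minus age, and 13.3 to 16.0 under the alternative equation. This part is firm under both equations.

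The effect on the trial is conditional. It arises only if the cap is applied, and only for participants who reach 85% before fatigue or unstable gait. For them, VO2 peak would be understated and cardiovascular training would fall below its labelled percentage of maximum. The size cannot be calculated without r and the share capped. The consequence is confined to the cardiovascular prescription, the check on training intensity and a secondary outcome. The primary chair-rise outcome and 1-RM are not directly affected.

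**What to change.** - In Section IV.C and in the endpoint paragraph of Section IV.D.2, state that the 85% heart-rate stop applies only to the cardiac-screening GXT.
- State that the VO2 tests at baseline, week 13 and week 23 all run to volitional exhaustion, subject to the safety stops already listed in the endpoint paragraph, which stay unchanged.
- Record the reason that each VO2 test ended, so that the VO2 peak label can be interpreted.
- Correct the reference to section 4.1.2b.

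The cost is protocol wording, one field on the test record, and confirmation of the stopping rule by the supervising clinician. No added test is part of this change. It relies on the baseline VO2 test already being separate from the GXT, as the maximal aerobic power paragraph indicates. If the investigators find that it is not, that is a design decision outside this wording change.

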## **5. Venipuncture:**

Laboratory analyses will include: CBC, CMP at procedure visit #1 only.

HIV antibody for participants that are not known to be HIV+ if no HIV testing available within the past 1 year.

Fasting IGF-I, IGF-BP3, total/free testosterone, IL-6, sTNFRI and sTNFRII, insulin and glucose will be evaluated at procedure visits #1 and #2, and at week 14, at least 48 hours following the last exercise session.

Inflammatory markers (IL-6, sTNFR-1, and TNF-alpha) will be measured pre-exercise, and 0, 60, or 90 minutes, and ~ 24 hours after a high-intensity exercise stimulus at week 2, 12, and 24.

For the optional microbiome substudy, EDTA plasma samples will be assessed for LPS, heparin plasma samples for sCD14, iFABP) and CRP. LPS levels will be measured using the Limulus Amebocyte Lysate (LAL) assay (Lonza, Switzerland) with plasma samples diluted 1:10 in endotoxin free water and heat-inactivated at 80°C for 15min. Commercially available ELISAs will be used to evaluate levels of IL-6, sCD14, and iFABP (all R&D Systems, Minneapolis, MN). Serum LBP levels were assessed using a custom ELISA all as reported in Dillon 2014.

Peripheral blood mononuclear cells (PBMCs) will be collected at each of the pre-exercise acute visits (weeks 2, 12, and 24) and stored. Future analyses (pending funding) will include an assessment of markers of T-cell and B-cell activation

Samples will be stored for additional analyses. These assays will be performed from stored specimens (in batch to minimize inter-assay variability) in the Clinical Translational Research Center (CTRC) core laboratory at UCD or by [name] in [name] laboratory. **All participant samples will be drawn between 7:30-10am. We will draw approximately 70 mL at the initial visit and 75 mL at the subsequent 3 visits.**

Risk: There is a small risk of local hematoma or infection associated with blood sampling.

Plans to minimize risk: The risks of hematoma and infection are minimized by having trained clinical personnel perform the procedures using sterile techniques.

Justification: We will be evaluating the response of HIV+ vs HIV- individuals to an exercise intervention, in hormone levels and markers of inflammation. Additional samples will be collected for storage. These safety and efficacy markers will be imperative in the design of future, larger intervention studies of exercise in HIV.

## **6. Intravenous line placement:**

For the acute exercise visits at weeks 2, 12, and 24, participants will have the option of having an intravenous line (IV line) placed rather than having venipuncture at the 4 time points. The same studies outlined above will be drawn. The participant does not have to have the same procedure at each of the acute visits (ie, can have 4 venipunctures at one and then opt to have the IV line at the next visit).

Risk: There is a small risk of a local hematoma, infection, superficial blood clot formation, or inflammation of the vein associated with intravenous catheter placement.

Plans to minimize risk: The risks of hematoma and infection are minimized by having trained clinical personnel perform the procedures using sterile techniques.

Justification: Some participants express a desire to have an IV placed rather than undergoing 4 venipunctures, while others note that they would not want an IV line while exercising. We will allow either to meet participant preference.

## **7. HIV testing.**

Risk: A positive HIV test may be identified during routine screening.

Plan to Minimize Risk: [name] is an HIV care provider in the Infectious Diseases Clinic and is trained in the counseling of new HIV+ patients, linkage to care of newly identified HIV+ patients, and care of HIV+ patients. If a person is identified as HIV+, she will directly provide counseling on the diagnosis and ensure that the participant is linked to care. As the study is restricted to HIV- or HIV+ on antiretroviral therapy for 2 years, that individual will no longer be eligible for study participation.

Justification: Every adult should have an HIV test at least once, thus HIV testing is often a part of routine clinical care. Because our outcome is focused on differences between HIV+ and HIV-, it is imperative that we correctly categorize subjects.

## **8. Questionnaires and other assessments:**

Food and nutrition. The "All-Day" screen for fruit and vegetable consumption will be administered at procedure visits #1 and #2. Additionally, a 3 day diet record will be provided the patient at baseline and 24 weeks. Analysis of 3 day diet record and correlation and quantification of dietary fiber intake will be performed by the Nutrition section of the CCTSI in collaboration with [name]. Participants that provide stool samples will also complete the Diet History Questionnaire. This will be completed at Acute Visit #1 while participants are waiting for the post-exercise blood draw.

QoL and depression. QoL and depressive symptoms, using the Medical Outcomes Study 36-Item Short-Form Health Survey (SF36), and Centers for Epidemiologic Studies Depression (CES-D) Questionnaire, respectively, will be assessed at procedure visits #1 and #2 and week 12.

Body Image Ideals Questionnaire. This questionnaire derives from a “self-discrepancy theory” where body-image satisfaction will depend upon (1) the extent to which an individual believes that his/her physical characteristics match his/her physical ideals, and (2) the importance associated with having or attaining those ideals.

Physical activity, life space, sedentary time, and wake/sleep time. The International Physical Activity Questionnaire (IPAQ) will be used to assess self-reported physical activity and sedentary time at weeks 0, 4, 8, 12, 16, 20, 24. Changes in spatial mobility will be measured using the Life-Space Assessment (LSA) Questionnaire[148], which is a modification of the original life space questionnaire developed by Stalvey et al.[149]. The LSA assesses the range, independence, and frequency of movement, is highly reproducible, and is sensitive to changes over a 6 mo. period[148]. Participants are queried about the number of times of the previous 4 weeks that they have travelled outside of the bedroom (or room that they sleep), and life-space is evaluated in series of levels (bedroom, other rooms in the home, outside house, within neighborhood (~1/2 mile), within town/city (5 mile), and outside town/city) radiating from that room.

Sedentary time and sleep quality will be measured using two tools. Actiwatch Spectrum, accelerometers to collect physical activity and wake/sleep time through additional sensors for light and dark, will be worn for 1 week between the 1st procedure visit and the first exercise visit, and for 1 week between the week 24 and the procedure visit #2.

Accelerometers have been calibrated in [name] laboratory at Rush University, and data will be analyzed in conjunction with her laboratory. We will assess change in sedentary time and change in sleep using the actiwatch. The Pittsburgh sleep index and the Munich Chronotype will assess usual sleep habits and restfulness following sleep.

In addition, each participant will be provided with a pedometer (*Omron Tri-Axis USB Pedometer, HJ-324U*) to wear every day through the study to monitor overall activity patterns and changes with an exercise intervention. This monitor stores 22 days of data. The participant will be asked to bring the monitor every other week and data will be downloaded during the exercise session.

Evaluation of health status, medication use, and falls. A brief health status questionnaire will be completed by participants every 2 weeks to document potential study-related problems/concerns (e.g., exercise discomforts); changes in health status (e.g., hospitalizations), prescription and over-the-counter medications (including non-steroidal anti-inflammatory agents); and falls. The surveys will be reviewed by the study nurse and appropriate follow-up pursued.

Post-intervention follow-up. Participants will be contacted by phone 3 months following study completion. Continued frequency of exercise/physical activity (IPAQ), intent to continue exercising, overall well-being will be assessed.

Risk: A person with a very high depression score may be identified on the CES-D depression screening questionnaire.

Plans to minimize risk: CES-D questionnaires will be briefly reviewed prior to the study participant leaving the visit. If an individual indicates a risk for suicidal ideations or intent on the CES-D, the participant will be referred immediately to their primary care provider or the emergency room.

Sample collection: Stool samples will be collected from participants at the first procedure visit (baseline) and second procedure visit as described above. Participants will be given a sample container and a biosafety bag and asked to give a sample within 72 hours prior to the procedure visit and store it in their freezer in the biosafety bag. The samples will be collected by [name] who will transfer to a -80 degree freezer in the 11th floor RC-2 lab for future analyses (pending future funding).

Risk: There a small risk of embarrassment due to collection and handing in stool samples.

Justification: The microbiome of stool can provide valuable data on dietary intake, and is hypothesized to play a role in the inflammatory profile of older adults with or without HIV infection. To understand the actual components of the microbiome, stool specimens or rectal swabs are required. Stool specimens are less invasive for participants, and thus will be utilized for collection for future studies.

**Confidentiality and privacy:** The use of questionnaires, interviews, and collection of personal medical information poses a risk to confidentiality and privacy and may cause embarrassment. These risks will be minimized by not including personal identifying information on the forms, when possible, and by conducting interviews and collection of personal information in a private setting. We will be using the REDCap, a Web-accessible database platform, to store data in a manner compliant with IRB and HIPAA standards for security. Data are backed up regularly and automatically and changes to data are logged, creating an audit trail indicating which data were changed, by whom, and when. REDCap is offered to investigators and supported through the CCTSI.

9. Focus group discussions (main study and sub-study participants). Participants will be interviewed in a quiet conference room with round-table seating, located on the Anschutz Medical Campus for convenience. Focus group interviews will be conducted in group sessions, with up to 8-12 HIV-infected participants in each group. We estimate 3 group interviews with ~ up to 24 participants total for current exercise study participants, and up to 5 group interviews for HIV-infected participants not currently exercising (anticipate 6 group sessions: 1 noon and 1 evening meeting for women, 1 noon and 1 evening meeting for non-exercising men, 1 noon and 1 evening meeting for exercising men). Because recruitment for K23 AG050260 is targeting initial recruitment of HIV-infected participants, Aim 1 will focus on HIV-infected participants only. Interviews will be audio-recorded and will last up to 120 minutes. Additional individual interviews lasting 30-60 minutes with select participants (up to 8) with unique perspectives may be conducted. We will continue interviews until further interviews are felt unlikely to provide novel themes.

Risk: The main risk with the discussion groups is confidentiality.

Plan to minimize risk: Participants will have completed the full study consent prior to enrollment (if in the main study), and will complete an additional consent if interested in the qualitative assessments. All the data generated from the study will be kept strictly confidential. Group interviews will be conducted among HIV-infected participants only. Participants will be notified clearly in the consent and prior to scheduling the focus group sessions that all involved participants will be HIV-infected, and therefore their HIV status will be known to others. Participation within the focus groups will be entirely voluntary. All data will be collected using unique patient identification codes.

Justification: We will integrate the qualitative input that is not readily captured in a close-ended questionnaire to understand the self-reported, individual reasons for initial engagement in exercise outside of the on-going study, motivating factors for study participation and engagement, and continuation of exercise after completion of the intervention. The addition of qualitative methods will provide insight into the aspects of health and wellness that are most valued by persons who are aging with HIV infection. The addition of the qualitative interviews allow each participant the opportunity to share his/her personal experiences, and gain insights from those that were unable or uninterested in joining the exercise study.

